9.0 STATISTICAL ANALYSIS PLAN

9.1 Statistical Analysis Plan Summary

The primary objective is to determine whether pembrolizumab is an effective therapy in uveal melanoma. The null hypothesis is that the objective response rate (ORR; percentage of patients achieving a confirmed CR or PR) is not attractive (defined as $\leq 5\%$). The alternative hypothesis is that the response rate is of interest for further development (defined as $\geq 20\%$).

Product: MK-3475
Protocol/Amendment No. 03

The final analysis of the overall response rate will be performed with a power of 80% with one sided $\alpha=0.05$. It is calculated that at least 4 responses are needed out of a total of 29 patients to reject the null hypothesis.

To allow early termination of the trial due to lack of efficacy, the trial will be conducted in two stages per Simon's Optimal Design. If no responses are demonstrated in the first 10 patients, then the trial will be terminated early for futility. If ≥ 1 responses are observed, enrollment will continue to 29 patients. Notably, in the absence of ≥ 1 response, if ≥ 2 patients experience stable disease (SD) for >24 weeks, then the study may proceed to stage 2 if the sponsor and PIs are in agreement. This provision was added since the probability of early termination was as high as 10% even with a response rate of 20%.

9.2 Statistical Analysis Plan

9.2.1 Sample Size Assumptions

To determine the overall sample size and the interim sample size, a two stage Simon's Optimal design was evaluated. To test the hypotheses (ORR=5% vs. 20%), 1 response from the first 10 subjects would be required to progress to stage 2 and a total of 29 subjects will be needed to achieve the desired type I ($<5\%$) and type II error rate (Power $>80\%$). The risk of prematurely stopping the trial after stage I if the drug is effective is approximately 10%. To reduce this risk, we will include the condition that if 2 or more patients experience stable disease for at least 24 weeks then the trial will proceed to stage 2.

Table 11: Sample Size Calculations

If the True Response Rate to pembrolizumab is: (%)	Probability of Early Termination after Stage I	Probability of Rejecting the Null Hypothesis
5%	0.599	0.047 (type 1 error)
10%	0.349	0.289
15%	0.197	0.589
20%	0.107	0.801
25%	0.056	0.913
30%	0.028	0.963

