2.2 Trial Design

2.2.1 Summary of Trial Design

This is an open-label, two stage, single arm pivotal study of intravenous (IV) pembrolizumab in patients with advanced or metastatic uveal melanoma. The primary endpoint of the study will be objective response rate (ORR). Other endpoints include progression-free survival (PFS), overall survival (OS), response duration, safety, and correlation of response rate with biomarkers (GNAQ/GNA11 mutational status, PD-L1 expression).

The study will enroll 10 patients in stage I of this two stage design; if one or more responses occur, an additional 19 patients will be enrolled. The sample size was designed to test whether pembrolizumab has a $\geq 20\%$ response rate in uveal melanoma with a clinically uninteresting response rate of 5%. In addition, if ≥ 2 patients experience stable disease (SD) for > 24 weeks, then the study may proceed to stage 2 if the sponsor and PIs are in agreement.

The primary objective of the study is to evaluate the activity of pembrolizumab in terms of ORR. The overall type I error rate for this study is strictly controlled at 5% (two-sided) and the study has a power of 80%. The study is considered to be positive if at least 4 patients treated with pembrolizumab have an objective response (of 29 subjects enrolled). All patients receiving pembrolizumab will receive pembrolizumab as IV infusion at a dose of 200mg every 3 weeks until disease progression, intolerable toxicity, confirmed complete response,

withdrawal of consent, or they require another form of antineoplastic therapy as determined by the Investigator.

We anticipate an accrual rate of 1 to 2 patients per month from 3 participating centers.

After the baseline tumor evaluation, tumor assessment during the study will be performed by radiological scans every 6 weeks starting from Week 12 until Week 24. At the discretion of investigators, patients who remain on study after 24 weeks and are clinically stable may decrease imaging frequency to every 12 weeks in the following schedule:

- First scheduled disease assessment: week 12
- Disease assessments every 6 weeks from week 18-24
- Disease assessments every 12 weeks from week 36-96

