5.10 Clinical Criteria for Early Trial Termination

Early trial termination will be the result of the criteria specified below:

1. Quality or quantity of data recording is inaccurate or incomplete
2. Poor adherence to protocol and regulatory requirements
3. Incidence or severity of adverse drug reaction in this or other studies indicates a potential health hazard to subjects
4. Plans to modify or discontinue the development of the study drug
5. Lack of efficacy as defined by no responses in the first 10 patients AND <2 patients with stable disease at 24 weeks.

In the event of Merck decision to no longer supply study drug, ample notification will be provided so that appropriate adjustments to subject treatment can be made.

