9.2.2 Efficacy Endpoints

9.2.2.1 Primary Endpoint

Objective response rate (ORR) as defined by immune-related response criteria (irRC) will be the primary endpoint of the study. As mentioned, the primary hypothesis is that ORR of pembrolizumab in uveal melanoma will be 20%. We will enroll 10 patients in stage I to allow for early termination for futility. If no responses are observed the trial will be terminated. However, if ≥ 1 objective response occurs, OR if ≥ 2 patients experience stability of disease for ≥ 24 weeks, the trial will proceed to stage II.

Product: MK-3475

Protocol/Amendment No. 03

In stage II, an additional 19 patients will be enrolled. If ≥ 4 responses occur in all patients treated on stage I and stage II, the trial will be considered positive.

Of note, response rates by RECIST 1.1 criteria will also be assessed although irRC will be used for the primary endpoint.

ORR will be stratified by PD-L1 expression and *GNAQ/GNA11* mutation status (see section 8.2.2.3).

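### The stable-disease route into stage 2 is optional in two sections and automatic in two others, and Table 11 leaves it out, so type I error below 5% is not guaranteed (0.047 to 0.055)

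*Combined protocol and SAP*

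**What the plan says.** Five sections of the combined protocol and SAP govern the interim decision when there are no responses in the first 10 patients but at least two have SD.

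- Section 2.2.1 is discretionary: "stable disease (SD) for > 24 weeks, then the study may proceed to stage 2", subject to agreement between the sponsor and the PIs.
- Section 9.1 is discretionary, again with SD beyond 24 weeks: "then the study may proceed to stage 2 if the sponsor and PIs are in agreement".
- Section 9.2.1 is automatic: "if 2 or more patients experience stable disease for at least 24 weeks then the trial will proceed to stage 2".
- Section 9.2.2.1 is automatic: if at least two "patients experience stability of disease for ≥ 24 weeks, the trial will proceed to stage II".
- Section 5.10 lists as a ground for termination: "Lack of efficacy as defined by no responses in the first 10 patients AND <2 patients with stable disease at 24 weeks". This fits the automatic version.

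Sections 9.1 and 9.2.1 explain the route by the roughly 10% risk of stopping early when the true response rate is 20%. Table 11, directly below the paragraph in Section 9.2.1 that adopts the route, gives a type I error of 0.047 and early termination of 0.599 at ORR 5%, and power of 0.801 at ORR 20%. Section 2.2.1 claims strict control of type I error at 5%, and Section 9.2.1 claims a rate below 5%. The success bar is 4 or more responses in 29 however stage 2 was opened.

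**The concern.** This is the only planned interim efficacy decision. In the state described, a sponsor that declined to open stage 2 would comply with Sections 2.2.1 and 9.1 and breach Sections 9.2.1 and 9.2.2.1. The SD duration also varies: more than 24 weeks, at least 24 weeks, or SD at 24 weeks.

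Separately, Table 11 should describe the rule that the trial will follow. Any route that lets the trial continue after 0 of 10, with the final bar unchanged, can only raise the chance of rejecting the null and lower the chance of stopping. Each rejection figure in Table 11 is then a lower bound and each early-termination figure an upper bound. The plan weighs the route's benefit for an effective drug but never shows its cost for an inactive one, which is more patients treated before the trial ends.

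**Working it through.** **Inputs from the plan.** Stage 1 n = 10, stage 2 n = 19, stop on 0 of 10, reject at 4 or more of 29, null ORR 5%, alternative 20% (Sections 9.1, 9.2.1 and 9.2.2.1).

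**Assumed.** The overall rate *s* of SD lasting 24 weeks, because the documents give none for pembrolizumab in uveal melanoma. I use 10%, 15% and 20%. I add 28% as a proxy: Section 4.2.1 reports SD at 23 weeks in 28% of a retrospective ipilimumab series in uveal melanoma, alongside an ORR of 5.4%.

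**Step 1: reproduce Table 11.** With true ORR *p*:

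- Early termination = (1−p)^10
- Rejection = Σ over x = 1 to 10 of P(Bin(10,p) = x) × P(Bin(19,p) ≥ 4−x)

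The last column is the ceiling if stage 2 is always opened, P(Bin(29,p) ≥ 4).

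| ORR | Early termination: plan / recomputed | Rejection: plan / recomputed | Ceiling |
|---|---|---|---|
| 5% | 0.599 / 0.5987 | 0.047 / 0.0468 | 0.0548 |
| 10% | 0.349 / 0.3487 | 0.289 / 0.2889 | 0.3290 |
| 15% | 0.197 / 0.1969 | 0.589 / 0.5891 | 0.6513 |
| 20% | 0.107 / 0.1074 | 0.801 / 0.8011 | 0.8596 |
| 25% | 0.056 / 0.0563 | 0.913 / 0.9130 | 0.9545 |
| 30% | 0.028 / 0.0282 | 0.963 / 0.9634 | 0.9879 |

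All six rows match the plain design, so the table contains no SD route.

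**Step 2: add the route.** Let q = P(Bin(10, s/(1−p)) ≥ 2), the chance of two or more SD patients given no responses. Let *u* be the chance that the route is used when open (u = 1 if automatic).

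- Early termination = (1−p)^10 × (1 − u·q)
- Rejection = plain value + u·q × (1−p)^10 × P(Bin(19,p) ≥ 4)

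The largest possible increments (u·q = 1) are:

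- ORR 5%: 0.5987 × 0.0132 = 0.0079, so type I error can reach 0.0548 (0.046829 + 0.007925 unrounded).
- ORR 20%: 0.1074 × 0.5449 = 0.0585, so power can reach 0.8596.

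**Step 3: route always used (u = 1).** The disputed state has probability (1−p)^10 × q. Expected N = 10 + 19 × (1 − early termination).

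At ORR 5%:

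| SD rate | q | Disputed state | Early termination | Type I error | Expected N |
|---|---|---|---|---|---|
| no route | – | – | 0.599 | 0.0468 | 17.6 |
| 10% | 0.284 | 0.170 | 0.428 | 0.0491 | 20.9 |
| 15% | 0.484 | 0.290 | 0.309 | 0.0507 | 23.1 |
| 20% | 0.655 | 0.392 | 0.206 | 0.0520 | 25.1 |
| 28% (proxy) | 0.842 | 0.504 | 0.094 | 0.0535 | 27.2 |

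At ORR 20%:

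| SD rate | q | Disputed state | Early termination | Power |
|---|---|---|---|---|
| no route | – | – | 0.107 | 0.801 |
| 10% | 0.361 | 0.039 | 0.069 | 0.822 |
| 15% | 0.585 | 0.063 | 0.045 | 0.835 |
| 20% | 0.756 | 0.081 | 0.026 | 0.845 |

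**Step 4: where 5% is passed.** Type I error equals 0.05 when u·q = (0.05 − 0.046829) / 0.007925 = 0.400. That is an SD rate of about 12.8% if the route is always used, or about 25.8% if it is used half the time. At half use, type I error is 0.0480, 0.0487 and 0.0494 for SD rates of 10%, 15% and 20%.

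**The case against.** Table 11 can be defended as the base Simon design, with the route added openly and fewer early stops as its declared aim. It is true that the arithmetic is right and the aim is stated. But the table is not labelled as excluding the route, it follows the paragraph that adopts the route, and it presents 0.047 as the trial's type I error.

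The type I excess is also small. It is at most 0.48 points above 5%, and there is none at an SD rate of 10%. That stands, and this part alone would be minor.

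The sections are not evenly split either: 5.10, 9.2.1 and 9.2.2.1 all fit an automatic route. That is correct, but no order of precedence is given, and Section 9.1 is the SAP's own summary.

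The difference between more than and at least 24 weeks is mostly cosmetic. It matters if the stricter wording is read as needing a scan after week 24, because under Section 2.2.1 the next routine scan may be at week 36.

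Finally, the SD rates are assumed. The one nearby figure in the documents, 28%, comes from another drug and a retrospective series. It lies above the assumed range and makes the loss of futility stopping larger.

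**Conclusion.** The concern holds and should be fixed. The contradiction over opening stage 2 rests on the text alone and needs no assumption. If the drug is inactive, the disputed state has probability 0.17, 0.29 or 0.39 at assumed SD rates of 10%, 15% or 20%.

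Table 11 describes a different rule from the one adopted. One-sided type I error is 0.047 to 0.055, whatever the SD rate and however the discretion is used, so the claims of control at 5% are not guaranteed; whether 5% is actually exceeded depends on both. Power is understated, not lost. The larger practical consequence is that 0.599 is only an upper limit on the chance of stopping for an inactive drug.

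Section 2.2.1 calls the 5% two-sided and Section 9.1 one-sided. That is a separate defect and adds no weight here; the 4-of-29 bar fits only a one-sided 5%.

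**What to change.** 1. Reconcile Sections 2.2.1, 5.10, 9.1, 9.2.1 and 9.2.2.1 into one statement: whether the SD route is automatic or needs agreement, one SD duration, and the scan that establishes it.
2. Label Table 11 as excluding the SD route. Add the ceiling column from the working and figures at assumed SD rates. If the route stays discretionary, show the plain design and the always-used case as bounds. The working gives the 5% and 20% rows; the other rows, route always used, are (early termination / rejection):

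| ORR | SD 10% | SD 15% | SD 20% |
|---|---|---|---|
| 10% | 0.242 / 0.301 | 0.169 / 0.310 | 0.109 / 0.316 |
| 15% | 0.131 / 0.610 | 0.089 / 0.623 | 0.055 / 0.634 |
| 25% | 0.034 / 0.929 | 0.021 / 0.939 | 0.012 / 0.946 |
| 30% | 0.016 / 0.974 | 0.009 / 0.980 | 0.005 / 0.984 |

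3. In Sections 2.2.1, 9.1 and 9.2.1, state a nominal one-sided 5% level. Replace the strict-control claim in 2.2.1 and the below-5% claim in 9.2.1 with a one-sided type I error between 0.047 and 0.055, depending on use of the SD route.
4. Item 3 reports the excess without removing it. To keep the rate below 5%, the sponsor could require 5 or more responses when SD alone opened stage 2, but only if this is fixed before stage 1 results are known. Type I error would be at most 0.0468 + 0.5987 × 0.0020 = 0.0480. Power would lie between 0.801 and 0.8011 + 0.1074 × 0.3267 = 0.836.

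The cost is wording in five sections, plus a label and extra columns for one table. No patients are added, and the 4-of-29 bar stays unless item 4 is chosen.

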strategy in uveal melanoma. Second, uveal melanoma cell lines demonstrate PD-L1 expression. In a group of metastasis cultures of uveal melanoma cell lines, nearly all lines demonstrated PD-L1 expression which was further augmented with interferon- γ stimulation (11). Although very few patients with uveal melanoma have been treated with anti-PD-1 therapies or have been assessed for PD-L1 expression, this suggests that the PD-1/PD-L1 axis may be a functionally relevant mechanism of immune evasion in uveal melanoma. Third, to evaluate the functional consequences of PD-1 blockade, uveal melanoma cell lines were grown in culture with CD3+ T cells (12). In IFN- γ stimulated cell lines, the addition of anti-PD-1 caused a T cell activation and significant increase in IL-2 production by the CD3+ T cells. Additionally, T-cell activation was found to be promoted by RNA interference of PD-L1 in a co-cultured uveal melanoma cell line with CD3+ T cells (13). Fourth, early phase studies have suggested that PD-L1 expression correlates with response to anti-PD-1/PD-L1, even in cancers other than melanoma, lung cancer, and renal cell carcinoma. (16, 47, 48). Based on cell line experiments, at least a subset of uveal melanomas would be predicted to express PD-L1, potentially predicting benefit from pembrolizumab. Finally, ipilimumab has demonstrated benefit in patients with uveal melanoma. In a retrospective review 39 patients with metastatic uveal melanoma were treated with ipilimumab. ORR by IrRC was 5.4% with one complete response and one partial response. An additional 28% of patients demonstrated stable disease at 23 weeks demonstrating that immune checkpoint inhibition may be an effective therapeutic strategy in uveal melanoma (16).

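### Table 11 and the stated type I error below 5% describe the response-only Simon rule and leave out the stable-disease route into stage 2 that the text above the table adds

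*Combined protocol and SAP*

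**What the plan says.** The purpose of the two stages is given in section 9.1: "To allow early termination of the trial due to lack of efficacy, the trial will be conducted in two stages per Simon's Optimal Design". The response rule is that "If no responses are demonstrated in the first 10 patients, then the trial will be terminated early for futility", and at the end "at least 4 responses are needed out of a total of 29 patients to reject the null hypothesis". Section 9.2.1 bases the sample size on that rule: "To test the hypotheses (ORR=5% vs. 20%), 1 response from the first 10 subjects would be required to progress to stage 2".

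The SD route is then added in five places, in two forms:

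- **Binding.** Section 9.2.1: "if 2 or more patients experience stable disease for at least 24 weeks then the trial will proceed to stage 2". Section 9.2.2.1: "OR if ≥ 2 patients experience stability of disease for ≥ 24 weeks, the trial will proceed to stage II". The stopping criterion in section 5.10 agrees: "Lack of efficacy as defined by no responses in the first 10 patients AND <2 patients with stable disease at 24 weeks".
- **Discretionary.** Sections 2.2.1 and 9.1 allow stage 2 on this route only with the agreement of the sponsor and the principal investigators.

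The stated reason (9.1 and 9.2.1) is the roughly 10% risk of stopping after stage 1 when the true response rate is 20%. Table 11 gives early termination of 0.599 and type I error of 0.047 at a 5% response rate, and 0.107 and 0.801 at 20%. Section 9.2.1 states type I error below 5%. Section 2.2.1 says it is strictly controlled at 5%.

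Section 4.2.1 supplies the only long-lasting SD rate for a checkpoint inhibitor in this disease. For ipilimumab, beyond a 5.4% response rate, "An additional 28% of patients demonstrated stable disease at 23 weeks".

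**The concern.** An extra route into stage 2 lowers the chance of stopping early and raises the chance of a positive result, at every response rate. Table 11 shows neither effect, and the plan gives no operating characteristics with the route included.

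The threshold is also low against the plan's own data. Two of 10 is 20%, below the 28% quoted for ipilimumab, and no reason is given for choosing 2. On a drug with that SD rate, 2.8 of 10 patients would be expected to have SD.

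At stake is whether the design still does what section 9.1 says two stages are for. A drug at the null response rate that produces SD as often as ipilimumab would usually go on to enrol 19 more patients, while the plan tells its readers it would stop 60% of the time.

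**Working it through.** **Inputs.** Response rate p = 5% (null) or 20% (alternative); 10 patients in stage 1 and 29 in total; positive at 4 or more responses (sections 9.1 and 9.2.1). SD threshold 2 of 10 (9.2.1). SD rate s = 28% in addition to responders (4.2.1), then varied. Assumptions: patients are independent, each is a responder, has qualifying SD, or has neither, and the route is binding.

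**Step 1: reproduce Table 11 without the SD route.**

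- Early termination = (1 − p)^10. At 5%: 0.95^10 = 0.5987. At 20%: 0.8^10 = 0.1074.
- Rejection = sum over x = 1 to 10 of P(x responses in 10) × P(at least 4 − x responses in 19). At 5%: 0.0468. At 20%: 0.8011.
- All six rows agree with the table to three decimals, and 0/10 then 3/29 is confirmed as the Simon optimal design. The table is correct for the response-only rule.
- Expected sample size at 5%: 10 + 19 × (1 − 0.5987) = 17.6.

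**Step 2: add the SD route.** The trial now stops only with 0 responses and at most 1 SD. With q = 1 − p − s:

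P(stop) = q^10 + 10 × s × q^9

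At p = 5%, s = 28%, q = 0.67: 0.0182 + 0.0762 = 0.0944. Expected sample size is 10 + 19 × (1 − 0.0944) = 27.2.

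**Step 3: type I error.** After 0 of 10, a positive trial needs at least 4 responses in 19, which has probability 0.0132 at p = 5%. The added rejection probability is (0.5987 − 0.0944) × 0.0132 = 0.0067, so type I error is 0.0468 + 0.0067 = 0.0535.

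**Step 4: vary the SD rate (p = 5%, route binding).**

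| SD rate | Early termination | Expected N | Type I error |
|---|---|---|---|
| Table 11 (no route) | 0.599 | 17.6 | 0.047 |
| 10% | 0.43 | 20.9 | 0.049 |
| 15% | 0.31 | 23.1 | 0.051 |
| 20% | 0.21 | 25.1 | 0.052 |
| 28% | 0.09 | 27.2 | 0.054 |
| 40% | 0.02 | 28.6 | 0.0545 |

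Type I error passes 0.05 at an SD rate of about 13%. Its ceiling is the single-stage value with no futility stop: P(at least 4 of 29 at 5%) = 0.0548. If 28% is read as 11/39 (an assumption), the exact 95% interval is 15% to 45%. At 45%, q = 0.50 and P(stop) = 0.0010 + 0.0088 = 0.010.

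**Step 5: the other side of the trade (p = 20%).** At s = 28%, wrong stopping falls from 0.107 to 0.009. After 0 of 10, the chance of at least 4 in 19 is 0.545, so power is 0.8011 + (0.1074 − 0.0092) × 0.545 = 0.855. Over SD rates of 10% to 40%, power is 0.82 to 0.86.

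**Step 6: discretionary wording.** At p = 5%, s = 28%, P(stop) lies between 0.094 (agreement always given) and 0.599 (never). If agreement were given half the time (an assumption), it is 0.599 − 0.5 × (0.599 − 0.094) = 0.347, with type I error 0.0502.

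**The case against.** Four points on the other side carry weight.

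- **The wording is not settled.** Sections 2.2.1 and 9.1 make the route discretionary, so two SD patients alone need not open stage 2. This stands. The 0.094 figure belongs to the binding wording in 5.10, 9.2.1 and 9.2.2.1. But Table 11 is exact only if the route is never used.
- **The 28% is a weak benchmark.** It is SD at 23 weeks from a small retrospective series, and the rate for SD lasting 24 weeks could be lower. This stands as a limit on size. Even at 15%, early termination is about half the tabulated value.
- **The type I excess is small.** It is bounded by 0.0548, and the final criterion of 4 of 29 is unchanged. This stands: the cost is mainly patients enrolled, not false-positive conclusions.
- **The plan reads the ipilimumab data as benefit.** Section 4.2.1 offers the 28% as a sign that checkpoint inhibition may work, although it also describes outcomes with ipilimumab and chemotherapy as poor. The plan sets no null for SD.

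A reader might therefore infer that the futility stop is switched off for any inactive drug, or that 2 of 10 is simply the wrong threshold. The documents do not support either. A null drug with a 10% SD rate still stops with probability 0.43, and an ipilimumab-like drug still stops about 1 time in 11. Whether SD at ipilimumab's rate should count as a reason to continue is a judgement the plan may make, provided it states and justifies it.

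**Conclusion.** The point holds as a mismatch between the stated rule and its stated operating characteristics. Table 11 is arithmetically right for a rule that the plan then modifies. With the route binding, a 5% response rate and the plan's own 28% SD figure, about 84% of the stopping probability is lost: (0.599 − 0.094)/0.599. The claims of type I error below 5%, or strictly controlled at 5%, fail once the SD rate reaches about 13%, though by half a percentage point at most.

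The loss of futility protection is the substantive harm. How large it is depends on the SD rate and on which wording governs, and neither can be fixed from the documents. What is established is that Table 11 and the 5% claims need correcting, and that the threshold of 2 lies below the plan's own ipilimumab figure without explanation. That the threshold must be raised is not established.

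**What to change.** 1. Choose one wording for the SD route and use it in 2.2.1, 5.10, 9.1, 9.2.1 and 9.2.2.1. If it stays discretionary, report results for agreement always given and never given.
2. Restate all rows of Table 11 with the route included, over a range of SD rates such as 10% to 45%, and add expected sample size.
3. Correct the 5% claims in 2.2.1 and 9.2.1: with the route binding, type I error can reach about 0.055.
4. Justify the 2-of-10 threshold against the 28% in 4.2.1, or reconsider it.

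Raising the threshold is only an option. For example, 5 of 10 at a 28% SD rate gives early termination 0.514, type I error 0.048, power 0.816, and wrong stopping at a 20% response rate of 0.081. But at a 15% SD rate wrong stopping is 0.105, against 0.107 with no rescue, so the route would do almost nothing. At 44% type I error is 0.051. Table 11 would still need restating.

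The cost of items 1 to 3 is text and one table, with no extra patients or procedures. The early-termination and type I figures become less favourable, while power at a 20% response rate rises to 0.82 to 0.86.
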